##### *Pregnancy Test and FSH*

β-Human Chorionic Gonadotropin (β-HCG) (women of child bearing potential only)

Follicular Stimulating Hormone (FSH) (post-menopausal women only)

#### Urinalysis

Glucose (GLUC)
Bilirubin (BILI)
Ketone (KETONES)
Specific gravity (SPGRAV)
Blood
pH
Protein (PROT)
Urobilinogen (UROBIL)
Nitrite
Leukocytes (WBC)
Microscopy, culture and sensitivity ( formal laboratory analysis if required )

#### Coagulation

Prothrombin Time (PT)
Activated Partial Thromboplastin Time (APTT)
International Normalised Ratio (INR)

#### Viral Screen

HIV 1/2 (anti-HIV1 and anti-HIV2 Ab)
Hepatitis B (HBsAg, anti-HBc [IgG + IgM if IgG is positive])
Hepatitis C (anti-HCV)

#### Biostatistical methods

##### *Listings*

All laboratory parameters and change from treatment baseline values will be presented in data listings. Values outside the laboratory reference range will be listed with flags if considered low or high for values outside the reference ranges (where applicable) and if values considered to be clinically significant by the investigator.

Pregnancy test data will be listed only, for all women. FSH data will be listed only, for all post-menopausal women.

Coagulation data as well as qualitative and quantitative urinalysis data will also be listed only.

##### *Tables*

Haematology, biochemistry and continuous dipstick urinalysis laboratory data will be summarised for each scheduled visit, including observed values, absolute change from treatment baseline.

Categorical dipstick urinalysis results will be summarised for each scheduled visit using frequency tabulations.

Numbers of participants with treatment-emergent abnormalities will also be shown.

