9.4 STATISTICAL ANALYSES

9.4.1 GENERAL APPROACH

Continuous variables will be summarised with the number of observations (non-missing values), mean, standard deviation (SD), median, quartiles, minimum and maximum. The minimum and maximum values will be presented to the same number of decimal places as recorded in the raw data. The mean, median and SD will be presented to one more decimal place than the raw data. Categorical variables will be summarised with the number of observations and the numbers and percent from each category. Percentages will be rounded to one decimal place, with the denominator being the number of participants in the relevant population with non-missing data. No missing data will be imputed. If required, confidence intervals (CIs) will be two sided and will use 95% confidence levels. Any analyses requiring significance testing will use a two-sided test at the 5% significance level.

The inoculation baseline will be defined as the last available assessment prior to administration of the malaria challenge agent. The IMP baseline will be defined as the last available assessment prior to the administration of the IMP. Unscheduled visits will be excluded from summary tables. Assessments conducted at Early Termination will be excluded from summary tables.

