9.4.4 SAFETY ANALYSES

All AE data will be listed for each participant, including severity, relationship to IMP (MMV367) and malaria challenge agent, relationship to other protocol-specific treatments, outcome and actions taken. In addition, listings of AEs leading to discontinuation, AESIs, SAEs and deaths, will be provided as applicable. Adverse events (AE) will be coded according to MedDRA and grouped by system organ class (SOC) and preferred term (PT).

Clinical laboratory parameters, physical examination results, vital signs, and 12-lead ECG results will be listed for all participants and visits. Summary tables for each scheduled visit, including observed values, change from each baseline and clinical significance of each abnormal value, will be presented.

Malaria clinical score data (total score and each sign/symptom individually) will be listed for all participants and visits.

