##### ***Biostatistical methods***

All vital signs data will be listed for all participants. Any values outside of the protocol defined normal ranges will be flagged, with clinical significance status presented for out-of-range results.

*Table 1: Vital Signs Normal Ranges*

Parameter	Range
Systolic blood pressure	90-140 mmHg
Diastolic blood pressure	50-90 mmHg
Heart rate	50-100 bpm
Temperature	35.0-37.5°C
Respiratory rate	10-25 breaths/min

Vital sign parameters will be summarised by presenting summary statistics for observed values and change from treatment baseline values for each scheduled visit.

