##### ***Biostatistical methods***

ECG parameters will be listed for all participants and visits. Triplicate ECGs will be presented in listings for individual readings as well as the mean for each triplicate. The triplicate means will be used for the summary table. Any values outside of the protocol defined normal ranges (Table XX) will be flagged.

*Table 2: ECG Normal Ranges*

Parameter	Range
PR interval	≤210 msec
QRS	50–120 msec
QTcF	Males: ≤450 msec Females: ≤470 msec

Observed values, as well as changes from treatment baseline, will be summarised descriptively for all ECG parameters by visit. An addition table will present the frequencies of participants who fulfill the following prolongation (change from baseline) criteria, considering all scheduled and non-scheduled visit data:

- QTcF prolongation >30
- QTcF prolongation >60
- QTcF >450 msec for males
- QTcF >450 msec for females
- QTcF >470 msec for females

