Inoculum Emergent Serious Adverse Events by MedDRA System Organ Class and Preferred Term (All Causalities)	FAS
Treatment Emergent Serious Adverse Events by MedDRA System Organ Class and Preferred Term (All Causalities)	IMP
Overall Summary of Inoculum Emergent Adverse Events of Special Interest (AESI)	FAS
Overall Summary of Treatment Emergent Adverse Events of Special Interest (AESI)	IMP
Inoculum Emergent Adverse Events of Special Interest (AESI) by MedDRA System Organ Class and Preferred Term (All Causalities)	FAS
Treatment Emergent Adverse Events of Special Interest (AESI) by MedDRA System Organ Class and Preferred Term (All Causalities)	IMP
Inoculum Emergent Adverse Events Leading to Study Discontinuation by MedDRA System Organ Class and Preferred Term (All Causalities)	FAS
Treatment Emergent Adverse Events Leading to Study Discontinuation by MedDRA System Organ Class and Preferred Term (All Causalities)	IMP
Summary of Concomitant Medications (FAS)	FAS
Summary of Concomitant Medications (IMP)	IMP
Haematology (Summary and Change from IMP Baseline)	FAS
Haematology (Categorical)	FAS
Biochemistry (Summary and Change from IMP Baseline)	FAS
Biochemistry (Categorical)	FAS
Urinalysis (Continuous) Results and Change from Baseline	FAS
Urinalysis (Categorical) Results	FAS

Vital Signs Results and Change from IMP Baseline	FAS
Abnormal Vital Signs Results	FAS
ECG Results and Change from IMP Baseline	FAS
ECG QTc Categorical Analyses	FAS
ECG Clinical Assessment	FAS
Malaria Clinical Score Summary by Question	FAS
Summary Peak Total Malaria Clinical Score and Time to Peak Total Malaria Clinical Score	FAS

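### The SAP tabulates haematology, biochemistry, vital-sign and ECG change only from the pre-MMV367 baseline, although the protocol requires change from each of two baselines

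*SAP*

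**What the plan says.** Protocol 9.4.1 sets two reference points. "The inoculation baseline will be defined as the last available assessment prior to administration of the malaria challenge agent", and "The IMP baseline will be defined as the last available assessment prior to the administration of the IMP". Protocol 9.4.4 then says of laboratory, physical-examination, vital-sign and ECG results: "Summary tables for each scheduled visit, including observed values, change from each baseline and clinical significance of each abnormal value, will be presented". Protocol 8.2.7 also has the investigator consider laboratory changes against inoculation, IMP dosing or both.

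SAP 4.2.2 carries both safety baselines over, as Inoculation Baseline and Treatment Baseline, using scheduled observations. The analysis sections then use only one:

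- SAP 11.3.3, laboratory tables: "Haematology, biochemistry and continuous dipstick urinalysis laboratory data will be summarised for each scheduled visit, including observed values, absolute change from treatment baseline". The laboratory listings likewise give change from treatment baseline only.
- SAP 11.3.4, vital signs: "summary statistics for observed values and change from treatment baseline values for each scheduled visit".
- SAP 11.3.7, ECG: "Observed values, as well as changes from treatment baseline, will be summarised descriptively for all ECG parameters by visit". The QTcF >30 and >60 prolongation criteria in the same section name no baseline.
- SAP Table B: the haematology title begins "Haematology (Summary and Change from IMP Baseline". The biochemistry, vital-sign and ECG titles match it, and all four tables are on the FAS.

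No SAP table or listing names change from inoculation baseline. SAP section 13 reports no change to the planned analysis.

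**The concern.** Safety of blood-stage infection is a secondary objective in its own right, separate from the safety of MMV367. The two baselines correspond to those two questions: the inoculation baseline isolates what infection does, and the IMP baseline what happens after the drug. The SAP keeps this pairing for adverse events (inoculum-emergent on the FAS, treatment-emergent on the IMP set) but drops it for measured parameters, where it also counts only treatment-emergent laboratory abnormalities.

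At stake is a paired summary of how liver enzymes, platelets, haemoglobin, vital signs and QTcF move between the uninfected state and Day 8, before any drug. That window shows infection without drug. The protocol's own risk section says that liver-enzyme abnormalities in earlier studies of this model were judged most likely due to malaria rather than to the investigational drug, so the distinction matters for interpretation.

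**Working it through.** There is no stated figure to reproduce, because the study has no formal sample-size calculation. The check compares the texts and counts visits in the Schedule of Activities.

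**Which value is the treatment baseline?** It is the last scheduled observation before MMV367. For haematology, biochemistry, vital signs and ECG that is Day 8 pre-dose. Protocol 12.1.5 expects most participants to be above 5,000 parasites/mL then.

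**What has a change value?** SAP 4.2.3 defines change as the post-baseline value minus the baseline value. Under a treatment baseline, Day 8 pre-dose is the reference itself and earlier visits have no change value.

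| Parameter | After inoculation, before MMV367 | After MMV367 | Pre-drug visits with a tabulated change |
|---|---|---|---|
| Haematology, biochemistry | 2 (Day 7 AM, Day 8 pre-dose) | 5 (24 h, 72 h, Days 15, 22, 27) | 0 |
| ECG | 1 (Day 8 pre-dose) | 4 (24, 48, 72 h, Day 27) | 0 |
| Vital signs | 6 (Day 0 post-inoculation, Days 4, 5, 6, 7 AM, Day 8 pre-dose) | all confinement and outpatient time points | 0 |
| Urinalysis | none scheduled | Day 27 only | not applicable |
| Weight | none (full examination at screening and end of study only) | Day 27 only | not applicable |

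For urinalysis and weight, the last scheduled value before MMV367 is also the last before inoculation. The two baselines are the same number, so the point does not apply to them.

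**What is lost?** For each participant and visit:

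change from inoculation baseline = change from treatment baseline + (treatment baseline − inoculation baseline).

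The bracketed term is the pre-drug infection shift, and the SAP never summarises it. Its mean can be recovered by subtracting the tabulated visit means if the same participants contribute to both. Its spread cannot. With equal visit standard deviations SD and within-person correlation r (both assumed, as the documents give neither):

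SD of change = SD × √(2(1 − r)).

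- r = 0.3: SD × √1.4 = 1.18 × SD
- r = 0.9: SD × √0.2 = 0.45 × SD

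The spread of the paired shift is thus uncertain by a factor of about 1.18 / 0.45 = 2.6 over this range. Its median and range are also unavailable from the tables.

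**Undosed participants.** Protocol 7.1 allows an inoculated participant to go undosed, for example after a serious or severe adverse event. Such a participant is in the FAS but has no treatment baseline, so contributes no change value to tables labelled FAS.

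**Consistency with the haemoglobin AESI.** That rule counts a fall of more than 20 g/L from the eligibility visit, a pre-inoculation reference. As a purely hypothetical series, 140 g/L at eligibility, 128 at Day 8 and 118 at Day 15 gives 140 − 118 = 22, an AESI. The change table would show 128 − 118 = 10.

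**The case against.** The strongest reply is that nothing decisive depends on the missing column. The infection-safety endpoint is the incidence, severity and relatedness of adverse events plus the malaria clinical score. Inoculum-emergent events are counted from inoculation and tabulated on the FAS, as are the clinical score and its peak. The haemoglobin AESI keeps its own pre-inoculation reference, so the hypothetical case above would still be reported. Observed values are summarised at every scheduled visit, laboratory values are listed with out-of-range and clinical-significance flags, and no more than 18 participants receive MMV367, so a reader can work out individual shifts by hand. The study is descriptive, and protocol section 9 leaves detail to the SAP. The documents expect absent or mild to moderate symptoms by Day 8 and predict no laboratory shift, so the missing changes may be small. Undosed participants may number zero, and their early-termination assessments are excluded from visit summaries by a separate rule.

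Most of this stands, and it limits the consequence. A reader might infer that the infection-safety objective itself is measured from an infected baseline; the endpoint definition and the inoculum-emergent tables show otherwise. A reader might also expect Day 0 to Day 7 visits to appear as changes before baseline; SAP 4.2.3 excludes that. Nor is every listing and table tied to the treatment baseline: the continuous urinalysis title names no baseline, and the vital-sign and ECG listings plan no change value.

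The reply does not remove the contradiction. Leaving detail to the SAP does not cover dropping a summary the protocol specifies, particularly when section 13 says nothing changed.

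**Conclusion.** The protocol and SAP conflict, and the SAP does not declare it. For haematology, biochemistry, vital signs and ECG, the paired shift from uninfected baseline to Day 8 is not tabulated: two laboratory time points, one ECG and six vital-sign assessments have no change value. Undosed FAS participants have no change value at any visit. The effect is confined to change summaries that support the infection-safety objective. The adverse-event, AESI and malaria-clinical-score analyses are unaffected, and mean shifts remain approximately recoverable. The size of the shifts cannot be stated from the documents.

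This rests on reading the SAP's treatment baseline as the scheduled Day 8 pre-dose value and on the visit schedule as printed. The point is worth correcting before database lock because the correction is cheap, but it does not threaten any endpoint.

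**What to change.** - Add change from inoculation baseline, at all post-inoculation visits, to the FAS haematology, biochemistry, vital-sign and ECG tables and to the laboratory listings. Before dosing all participants share the same exposure, so the all-participants column is the natural place to read the pre-drug shift.
- Present change from treatment baseline on the IMP set, for post-dose visits only.
- State which baseline the QTcF >30 and >60 ms categories use, and ideally report both. Day 0 ECGs are scheduled in triplicate and Day 8 ECGs are not, so the choice also affects the precision of the reference.
- Align the Table B titles and analysis sets.
- Leave urinalysis and weight as they are; a second column would duplicate the first.

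If the sponsor prefers the single baseline, SAP section 13 should declare the departure from protocol 9.4.4 and justify it.

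The cost is a second change column in existing programs and revised table titles. No new data are needed, and both baselines are already defined in SAP 4.2.2.

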#### **11.3.4 Vital Signs**

##### **Parameters**

- Systolic Blood Pressure (SBP) (mmHg)
- Diastolic Blood Pressure (DBP) (mmHg)
- Heart Rate (beats/minute)
- Body Temperature (°C)
- Respiratory rate (beats/min)

##### ***Biostatistical methods***

All vital signs data will be listed for all participants. Any values outside of the protocol defined normal ranges will be flagged, with clinical significance status presented for out-of-range results.

*Table 1: Vital Signs Normal Ranges*

Parameter	Range
Systolic blood pressure	90-140 mmHg
Diastolic blood pressure	50-90 mmHg
Heart rate	50-100 bpm
Temperature	35.0-37.5°C
Respiratory rate	10-25 breaths/min

Vital sign parameters will be summarised by presenting summary statistics for observed values and change from treatment baseline values for each scheduled visit.

#### **11.3.5 Body Measurements**

##### ***Definition of variables***

- Height (Screening Only)
- Weight
- Body mass index (BMI)

##### ***Biostatistical methods***

Body measurement data will be listed for all participants and visits, including height, weight and Body Mass Index (BMI) which is auto-calculated within the CRF.

Observed values, as well as changes from treatment baseline, will be summarised descriptively for weight and BMI by visit.

#### **11.3.6. Physical Examination**

##### **Parameters**

• Weight	• Skin
• HEENT (Head, Eyes, Ears, Nose, Throat)	• Neurological / Reflexes
• Height (screening only)	• Heart / circulation
• Chest / Lungs	• Neck
• Abdomen	

### ***Biostatistical methods***

Physical examination findings will be listed for all participants and visits.

#### **11.3.7. 12-lead ECG**

##### **Parameters**

- PR interval (msec)
- QRS interval (msec)
- QTcF interval (msec)
- Overall ECG assessment (Normal, Abnormal)
- ECG abnormality (specify as appropriate)
- Clinical Significance

##### ***Biostatistical methods***

ECG parameters will be listed for all participants and visits. Triplicate ECGs will be presented in listings for individual readings as well as the mean for each triplicate. The triplicate means will be used for the summary table. Any values outside of the protocol defined normal ranges (Table XX) will be flagged.

*Table 2: ECG Normal Ranges*

Parameter	Range
PR interval	≤210 msec
QRS	50–120 msec
QTcF	Males: ≤450 msec Females: ≤470 msec

Observed values, as well as changes from treatment baseline, will be summarised descriptively for all ECG parameters by visit. An addition table will present the frequencies of participants who fulfill the following prolongation (change from baseline) criteria, considering all scheduled and non-scheduled visit data:

- QTcF prolongation >30
- QTcF prolongation >60
- QTcF >450 msec for males
- QTcF >450 msec for females
- QTcF >470 msec for females

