5 STUDY POPULATION

5.1 INCLUSION CRITERIA

Volunteers must fulfil all of the following criteria to be eligible for inclusion in this trial:

Demographics and general considerations

1. Healthy adults aged 18 to 55 years inclusive who will be contactable and available for the duration of the trial and up to two weeks following the EOS visit.
2. Total body weight greater than or equal to 50 kg, and a body mass index (BMI) within the range of 18 to 32 kg/m² (inclusive). BMI is an estimate of body weight adjusted for height. It is calculated by dividing the weight in kilograms by the square of the height in metres.
3. Completion of the written informed consent process prior to undertaking any trial-related procedure.
4. Must be willing and able to communicate and participate in the whole trial.
5. Agreement to adhere to Lifestyle Considerations (Section 5.3) throughout the trial duration.

6. Must be able to provide contact details of a support person (responsible adult) who is aware of the participant's participation in the study and is available to provide assistance if required (for example with contacting the participant in the event that study staff are unable to, or with transporting the participant to and from the study site if required).

Vital signs and ECG parameters

7. Vital signs at screening (measured after 5 min in the supine position):
 - Systolic blood pressure (SBP): 90–140 mmHg,
 - Diastolic blood pressure (DBP): 40–90 mmHg,
 - Heart rate (HR): 40–100 bpm.
- Note: Symptomatic postural hypotension will be assessed by measuring SBP and DPB in the standing position (see exclusion criterion 10).
8. At Screening and pre-inoculation with the malaria challenge agent (Day 0), normal standard mean of triplicate 12-lead electrocardiogram (ECG) parameters after 5 minutes resting in supine position:
 - QTcF: ≤450 msec (males) or ≤470 msec (females),
 - QRS: 50–120 msec,
 - PR interval: ≤ 210 msec,
 - Normal ECG tracing unless the Principal Investigator or delegate considers an ECG tracing abnormality to be not clinically relevant.

Contraception

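### The QTc categorical table in SAP 11.3.7 is labelled change from baseline, but three of its five rows are absolute values, so an eligible woman unchanged at 451–470 ms is counted as prolonged

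*SAP*

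**What the plan says.** **ECG entry limits.** Protocol 5.1, criterion 8, applies to the mean of triplicate ECGs at Screening and Day 0: "QTcF: ≤450 msec (males) or ≤470 msec (females".

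**ECG categories.** SAP 11.3.7 gives a normal-range table with the same limits by sex. It then plans a further frequency table on "prolongation (change from baseline) criteria, considering all scheduled and non-scheduled visit data". The five rows are QTcF prolongation >30, prolongation >60 (no unit given), >450 ms for men, "QTcF >450 msec for females", and >470 ms for women. SAP Table B assigns the QTc categorical table to the FAS, which SAP 5.1.1 defines by receipt of the challenge agent, not of MMV367.

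**Baselines.** SAP 4.2.2 defines an inoculation baseline and a treatment baseline. SAP 11.3.7 summarises ECG change from treatment baseline by visit.

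**Laboratory data, for comparison.** SAP 11.3.3 plans counts of participants with treatment-emergent abnormalities. No such condition is written for ECGs or vital signs.

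**Vital signs.** Entry (Protocol 5.1, criterion 7, supine) allows "Heart rate (HR): 40–100 bpm" and "Diastolic blood pressure (DBP): 40–90 mmHg". After inoculation (Protocol 8.2.3 and SAP 11.3.4, seated) the normal ranges are HR 50–100 bpm and DBP 50–90 mmHg. SAP 11.3.4 says: "Any values outside of the protocol defined normal ranges will be flagged". Table B lists "Abnormal Vital Signs Results" without a counting rule.

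**The concern.** The label promises a change from baseline, and three rows do not measure one. One of those rows, women above 450 ms, lies 20 ms inside the range in which women may enter the trial. A reader of the table would take a count there as a finding after exposure, when it may only describe how the participant arrived.

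The groups are very small. Cohort 1 has 3, 2 and 1 participants at 20, 90 and 1500 mg, and SAP section 4 summarises by dose group. Within that cohort, one pre-existing case would show as 1/3, 1/2 or 1/1. Safety of MMV367 and safety of the infection are two of the four secondary objectives, so the table should separate what was present at baseline from what appeared after dosing.

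**Working it through.** The plan states no figure on this point, so there is none to reproduce. The check compares each absolute row with the entry limit and asks whether an eligible participant whose value never changes is counted.

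**Step 1: position of each row.**

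| Row | Entry limit | Distance inside limit |
|---|---|---|
| Men >450 ms | ≤450 ms | 450 − 450 = 0 |
| Women >450 ms | ≤470 ms | 470 − 450 = 20 ms |
| Women >470 ms | ≤470 ms | 470 − 470 = 0 |

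**Step 2: zero-change test.** A woman constant at 451, 460 or 470 ms is eligible and within the SAP normal range. Her change is 0, so she is in neither change row, yet she is in the >450 row. A man constant at 450 ms is eligible and not counted, because the row is a strict inequality. A woman constant at 470 ms is not in the >470 row. Only the female >450 row counts an unchanged eligible participant.

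**Step 3: which ECGs are in scope.** The schedules give seven ECG time points: Screening, Day 0, Day 8 pre-dose, 24, 48 and 72 hours, and end of study. Three of the seven precede MMV367. All scheduled and unscheduled data are to be used with no post-dose limit, so read literally these three are in. So are any repeat screening ECGs, which Protocol 5.4 allows. On the FAS, a participant inoculated but not dosed (Protocol 7.1) has no treatment baseline for the change rows but can still enter an absolute row.

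**Step 4: what a baseline condition would and would not remove.** This is an illustration on assumed distributions, because the documents contain no baseline ECG data. The assumptions are:
- eligible women, with no drug or malaria effect;
- mean QTcF 410–430 ms, between-person SD 15–20 ms, single-ECG SD 6–10 ms;
- eligibility on two triplicate means, then five single ECGs (pre-dose, 24, 48 and 72 hours, end of study).

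Results across the 12 settings:
- any QTcF >450 ms: 1.7% to 32%;
- post-dose >450 ms with pre-dose ≤450 ms: 1.0% to 17%;
- any QTcF >470 ms: 0% to 5.8%.

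Setting by setting, the share of the >450 rate that remains under the condition runs from 0.095/0.238 = 40% to 0.029/0.043 = 67%. What remains comes from repeated single readings. Triplicates are specified only at Screening and Day 0 (Protocol 8.2.5), so the Day 8 baseline is itself a single reading.

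**Step 5: vital signs, side by side.** The lower limits for HR and DBP are 40 at entry and 50 afterwards, a difference of 10 in each. The SBP entry range, "Systolic blood pressure (SBP): 90–140 mmHg", is the same as the later range. The entry reading is supine and the later ones are seated, so the two limits do not apply to the same measurement. No rate is calculated: the table has no counting rule and the documents give no baseline vital-sign data.

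**The case against.** The strongest reply is that this is a descriptive table in a trial of at most 18 people. Every ECG is listed individually, so a reader can see that a woman at 455 ms after dosing was also at 455 ms at Screening. The table contains two true change rows, and change from treatment baseline is summarised by visit. The ECG abnormal flag for women already uses 470 ms, the >470 row already exists, and QTcF above 480 ms is already an adverse event of special interest with its own tables. No test, dose decision or stopping rule is tied to these rows.

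All of that stands, and it limits the consequence. It does not make the label right or stop the female >450 row from counting an unchanged eligible woman. Listings let a reader undo the miscount; they do not correct the table.

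A reader might also infer three stronger things that the documents do not support:

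- **That every threshold at the entry limit has the same defect.** The men >450 and women >470 rows do not count an unchanged participant. Only noise, a real change or an out-of-limit pre-dose value reaches them.
- **That vital signs show the same fault.** The entry and later ranges differ, but so does posture. Flagged values carry a clinical-significance status, and how the table counts them is not stated.
- **That a false cardiac signal can be expected at some stated rate, or that a real one would be hidden.** Any rate depends on assumed distributions, and the change rows and listings remain to show a true effect.

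**Conclusion.** The point holds for the QTc categorical table. Followed as written, SAP 11.3.7 counts as prolonged an eligible woman whose QTcF is unchanged between 451 and 470 ms, including from an ECG before dosing, under a label that says change from baseline. This is a stated rule that gives a wrong count, and it follows from the documents without any assumption.

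Its size is not known. It depends on how many enrolled women have a QTcF in that 20 ms band. The figures in the working are illustrations only. They also show that a baseline condition would leave roughly half of the illustrated no-effect count, because that part is measurement noise. The effect is on a descriptive table, so this is a correction to consider, not a threat to an objective. The vital-sign ranges are a secondary matter of explanation and table definition, with no magnitude claimed.

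**What to change.** In SAP 11.3.7:

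- Keep the change-from-baseline label for the >30 and >60 rows only, and state the unit (ms) and the baseline (treatment baseline).
- Count a participant in an absolute row only if the value is post-dose and the treatment-baseline QTcF was at or below that row's threshold. Produce these rows on participants who received IMP.
- Show pre-dose exceedances in a separate column. The >450 row for women may stay under this condition.

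As a secondary step, the sponsor should reconcile or explain the different entry and post-inoculation ranges for HR and DBP, given the change of posture. The SAP should state the counting rule for the abnormal vital-signs table and present it by baseline category.

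The cost is SAP wording and table shells; all the values are already collected, and the approach matches the treatment-emergent count already planned for laboratory data. The small downside is that exceedances in participants already above a threshold at baseline move to the separate column. The condition does not remove noise from repeated single ECGs, and a footnote to the table should say so.
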